- a. A board-certified radiologist will interpret all images as required by the protocol. All reads will be interpreted in a blinded fashion. [name] would be the primary reader unless the sponsor requests a different physician.
- b. Summary images and image interpretations will be uploaded to the study-specific server site. All reads will be immediately available to the sponsors. Images and any interpretation data can be reviewed by site users as required by the protocol.
- c. The core lab will select images of interest during review. These will be immediately available for review by the sponsor or sponsor's designee from any web enabled device.
- d. The sponsor or any sponsor designee will have access to the entire imaging dataset once it has been validated for HIPAA compliance via download from our server. Our standard imaging turn-around time is 14 days from submission.

6. Imaging Data Reporting

- a. All imaging data collected during the trial will be saved on our secure database.
- b. Images and draft imaging reports are available via secure web access.
- c. These may be downloaded in PDF or excel format. These may also be downloaded in csv format to allow importing into other EDC systems.

Study Management and Oversight

Vanderbilt University Medical Center (VUMC) will serve as the coordinating center for this study. The VUMC team will be responsible for:

- Study protocol development and amendments
- Informed consent templates and revisions
- IRB approvals and correspondence
- Site initiation and training materials
- Case Report Forms (CRFs) and data collection tools
- Monitoring reports and audit documentation
- Adverse event and protocol deviation reporting
- Regulatory compliance (e.g., certifications, CVs, signature pages)
- Communication logs with participating sites
- Final study report and data safety monitoring documentation

Institutional review boards

The site investigator must submit this clinical protocol and subject informed consent form to the appropriate IRB. The study will not start at a clinical site and subjects will not be enrolled until a copy of written and dated approval/favorable opinion has been issued by the site.

Any amendment or modification to the clinical protocol must be sent to the IRB. The IRB must also be informed of any event likely to affect the safety of subjects or the conduct of the study. If the IRB imposes any additional requirements (e.g. safety reports, progress reports etc.), this will be followed, if appropriate.

A Data and Safety Monitoring Board (DSMB) will oversee participant safety and data integrity throughout the study. DSMB members will include experts in neuro intervention, biostatistics, and clinical trial execution. Their responsibilities will include:

- Reviewing safety and efficacy data at regular intervals
- Advising on study continuation, modification, or termination

Electronic Data Capture and Monitoring

VUMC will oversee data management using Redcap, a secure electronic data capture system. The system includes built-in checks to support data accuracy and protocol compliance. The Project Manager will conduct monthly data reviews to identify and resolve discrepancies. All study personnel will be trained in data entry procedures and Good Clinical Practice (GCP) standards.

The Project Manager (PM) will conduct monthly data reviews to identify outliers, inconsistencies, and missing information. Discrepancies will be addressed through open queries in REDCap and resolved in a timely manner to maintain data quality.

Staff Training: All study personnel involved in data entry and protocol implementation will receive training on the protocol, REDCap use, and Good Clinical Practice (GCP) standards.

Protocol Adherence Monitoring: Compliance will be assessed through monthly check-ins and quarterly oversight meetings. Any deviations will be documented, reviewed, and reported to the IRB as required.

References

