All investigators and sub-investigators will receive training on the above techniques prior to site initiation. Training will either be in-person or via video teleconference. Additionally, each site must confirm that they stock the Raptor, VacLok syringe, and Carrier navigation catheter prior to site initiation.

Objective and endpoints

Study objective

The object of this study is to compare the efficacy and safety of the Plunger technique vs static aspiration for direct aspiration thrombectomy using the Raptor aspiration catheter.

Primary effectiveness endpoint

The primary endpoint is the first pass effect (FPE), defined as TICI 2c or 3 after the first attempt of direct aspiration thrombectomy, as determined by core lab assessment (see p. 16)

Primary safety endpoint

The primary safety endpoint is the rate of symptomatic intracranial hemorrhage (sICH) at 24 hours, as defined by 1) new intracranial hemorrhage on CT and 2) neurologic deterioration associated with worsening NIHSS by 4 or more points.

Secondary endpoints

- Overall rate of TICI 2b or 3 recanalization with Plunger technique vs. static aspiration vs. rescue therapy. At least one thrombectomy attempt with the assigned technique will be made prior to rescue treatment with a stent-retriever or other device if needed.
- Functional outcome at 90 days based on modified Rankin scale (mRS) assessment. All patients will be contacted *by phone* at 90 days to assess their functional status.

- Rate of successful navigation of aspiration catheter to clot. This will be reported by the site investigator. If the aspiration catheter cannot be navigated to the clot then rescue treatment with a stent-retriever may be used.
- Rate of rescue treatment with stent-retrievers. This rescue therapy will be employed after **at least** one attempt with aspiration thrombectomy, or if the Raptor cannot be successfully navigated to the clot.
- Rate of complete clot ingestion. Sites will report if the clot is completely ingested through the Raptor and into the syringe, or if it is partially ingested in the tip of the Raptor.
- Recanalization rates with the two different sizes of Raptor: analyses will compare recanalization of the 0.071" vs. 0.074" sizes of Raptor.

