Patients with a large vessel occlusion who are clinically appropriate for thrombectomy will be screened for participation. Subjects who meet selection criteria below will be enrolled. Note that there are no parenchymal imaging criteria; site investigators will determine if individual patients will benefit from thrombectomy. The trial is not intended to assess clinical criteria for endovascular treatment decisions, but rather to assess *technique* of thrombectomy once that decision has been made.

Inclusion criteria

1. Acute ischemic stroke due to occlusion of the terminal ICA or M1 segment of the MCA
2. Treatment can be initiated within 24 hours of onset
3. Age of 18 years or older

Exclusion criteria

Evidence of acute intracranial hemorrhage prior to treatment

Failure to obtain informed consent

Subject withdrawal

Subjects enrolled in the study can discontinue their participation at any time for any reason without prejudice or reduction in the quality of their medical care. The investigator can terminate a subject's participation in the study to protect the subject's health. The Investigator must document this notification of withdrawal from the study in the appropriate CRF and notify the sponsor.

Data collection

Baseline data: At the time of endovascular treatment, the following data will be collected for all subjects:

- Age
- Baseline mRS
- ASPECTS score
- Hyperdense vessel sign (yes/no; site-reported)
- NIHSS
- Location of occlusion (right or left, ICA terminus or M1)

Procedure data: The following will be collected immediately after the procedure:

- Guide catheter used
- Which Raptor used (0.071" or 0.074")
- Microcatheter used (Carrier or other)
- Microwire used
- Successful navigation? (yes/no)

- Total duration of aspiration
- Total duration of plunging (if assigned to Plunger technique)
- Reperfusion (TICI) after each pass (site-assessed)
- Clot ingestion: none, partial, or complete
- Groin puncture time
- On-clot time
- Time of reperfusion
- Rescue treatment? If yes, what device and how many passes

24 hour data: To be collected at 24 hrs post-procedure +/- 6 hours:

- Imaging evidence of hemorrhage? If parenchymal, HI1, HI2, PH1, or PH2; or IVH, SAH, SDH
- Symptomatic ICH?
- NIHSS

90 day follow up: To be collected by phone at 90 days +/- 30 days

- Modified Rankin Score

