The primary endpoint is the first pass effect (FPE), defined as TICI 2c or 3 after the first attempt of direct aspiration thrombectomy, as determined by core lab assessment. The rate of successful FPE will be compared between the Plunger group and the static aspiration group per the mITT population as above.

Null hypothesis: the rate of successful FPE is not different between static and plunger aspiration. The rate of FPE will be compared between the two groups by chi-square analysis. If there is a significant difference between the two, then the null hypothesis will be rejected.

Analysis of primary safety endpoint

The primary safety endpoint is the rate of sICH at 24 hours compared between the static and Plunger aspiration groups. A chi-square test will assess for differences in rate of sICH between the two treatment groups in the mITT population. Secondary analyses will account for ASPECTs score and time to treatment between the two groups.

Analysis of secondary endpoints

Overall rate of TICI 2b or 3 recanalization with Plunger vs. static aspiration will also be compared using chi-square analysis on the mITT population.

For the following additional binomial secondary efficacy endpoints, treatment groups will be compared using logistic regression models as appropriate:

- Rate of successful navigation of aspiration catheter to clot
- Rate of rescue treatment with stent-retrievers
- Rate of complete clot ingestion
- Rate of recanalization by clot density on CT (hyperdense vs isodense)

The 90-day functional outcomes, including mRS and PROMIS-10, will be compared between the two groups using ordinal shift analysis.

Randomization

Patients will be randomized (1:1; permuted block randomization) once the decision is made for patient to go for thrombectomy using the REDCap randomization tool.

Adverse events

Throughout the course of the clinical investigation, all adverse events will be recorded on the applicable Adverse Event CRF. The date of onset, date of resolution, severity, and action taken will be evaluated by the Investigator. The relationship to the technique or device, relationship to the procedure, and clinical significance will be evaluated. The neurological outcomes and adverse events will be reported.

Adverse Event Classification and Definitions

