An Adverse Event (AE) is any untoward medical occurrence, unintended disease or injury, or untoward clinical signs (including abnormal laboratory findings) in subjects, users or other persons, whether or not related to the investigational procedure.

A Serious Adverse Event (SAE) is an AE that:

- Led to death
- Led to a serious deterioration in the health of a patient that:
 - 1) Resulted in a life-threatening illness or injury
 - 2) Resulted in a permanent impairment of a body function or body structure
 - 3) Required in-patient hospitalization or prolonged hospitalization
- Resulted in medical or surgical intervention to prevent permanent impairment to a body function or body structure
- Led to fetal distress, fetal death or a congenital abnormality or birth defect.

For the current study, detailed and narrative reports of the following specific adverse events will be obtained:

- Incidence of death 24 hours post procedure
- Vessel perforation
- Vessel dissection
- Failure to navigate to target

Adverse Event Assessments

Relatedness:

- Procedure-related: Event has a strong temporal relationship to the study procedure. This includes AEs attributable to any device(s) used at procedure, such as access devices, delivery microcatheters, non-ionic contrast, guidewires, or any other adjunctive, approved/cleared device for neurovascular procedures.
- Technique-related: Event has a strong temporal relationship to the use of aspiration for thrombectomy.
- Unknown: Event relationship cannot be attributed to any of the above categories and remains undetermined.

Event Reporting Requirements

Any adverse event that occurs during the course of the study must be recorded and reported using the appropriate Adverse Event eCRF. These will include events occurring from the point of consent until a subject exits the study. The Investigator must sign each AE eCRF report. Investigators must obtain all information available to determine the causality and outcome of the AE and to assess whether it meets the criteria for classification as serious and the relationship of each adverse event to the procedure or device.

Pre-existing medical conditions or symptoms occurring prior to the start of the procedure should not be reported as adverse events. In the situation where there is a worsening of a pre-existing medical condition or symptom due to a study related procedure, an adverse event should be reported.

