The Investigator is required to report all SAEs within 72 hours after first learning of the event. The primary method of reporting SAEs will be through the eCRFs. All SAEs will also be reported to the local IRB.

Site selection

Potential clinical sites will be assessed to ensure the investigator and his/her staff have the facilities, expertise required for the study and ability to conduct the study according to the clinical protocol.

To participate in this trial a clinical site must have, at a minimum, the following:

- 24/7 stroke interventional capabilities
- CT-based acute stroke imaging protocols (MRI is not acceptable)
- Ability to support timely data collection via an Internet-based EDC system
- Resources for conducting the informed consent process
- Willingness to adhere to the study protocol

Angiographic core lab

The procedural angiograms will be submitted by each site with all subject identifiers removed and only the assigned subject study number on the images. Each angiogram will be blindly assessed by the core lab for:

- Reperfusion score after first pass
- Reperfusion after final aspiration pass
- Reperfusion at end of procedure

Oculus Imaging, LLC, will serve as the core lab. The core lab services will include:

1. Trial Specific Website Design

- a. We will customize a user accessible website on our server specifically for the requested study. All imaging aspects of the study will be managed through this site.
- b. The primary functions of the site include electronic image submission, de-identification, and analysis.
- c. The website may also allow users or sponsors to review subject images and the dynamic trial reports as needed.
- d. Our study websites are secure, HIPAA, FDA, (CFR part 11) and E-Union compliant. Daily backups are performed.
- e. Studies are stored in at least two separate off-site archive sites.
- f. After launch of the trial website, any requested changes to the data collection for this trial may require a database change. Such requests would be reflected in a new version of the trial guidelines. Database changes may require revalidation of the trial imaging reports and additional fees may apply.

2. Imaging Protocol

- a. Oculus Imaging will write the Imaging Guidelines detailing imaging modalities to be used, imaging acquisition protocols, and procedures for image transfer.

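### The sICH definition has no death criterion, so a CT-proven haemorrhage that kills before any repeat NIHSS cannot count in the primary safety endpoint as written

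*Protocol*

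**What the plan says.** Under Objective and endpoints, Primary safety endpoint, the protocol states: "The primary safety endpoint is the rate of symptomatic intracranial hemorrhage (sICH) at 24 hours". Two numbered criteria follow, joined by an and: "new intracranial hemorrhage on CT and 2) neurologic deterioration", the second being completed as "neurologic deterioration associated with worsening NIHSS by 4 or more points". Death is not mentioned, and the NIHSS from which worsening is measured is not named.

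Under Data collection, the post-procedure items fall under "24 hour data: To be collected at 24 hrs post-procedure +/- 6 hours". They are the imaging evidence of haemorrhage with its type, a separate item "Symptomatic ICH", and NIHSS. The Schedule of assessments marks NIHSS at baseline and at 24 hours only.

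Under Adverse Event Classification and Definitions, death makes an event serious, and "Incidence of death 24 hours post procedure" is among the events that need a detailed narrative. Neither provision refers to sICH.

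Analysis of primary safety endpoint compares sICH rates between the groups by chi-square in the mITT population. It has no rule for a patient who dies before the second NIHSS.

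**The concern.** A haemorrhage that kills within hours is the clearest case of a symptomatic one. The written rule recognises symptoms only through a change in a score, and that score may never be taken again in such a patient. Applied literally, the rule can leave the worst outcomes out of the endpoint meant to capture them. If early fatal bleeds were commoner in one arm, that arm would look safer on this endpoint than it was.

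The separate sICH item adds an ambiguity. The endpoint could be the answer to that item, or it could be derived from the CT finding and the NIHSS values. The protocol does not say which, so the same fatal case could be counted at one site and not at another.

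**Working it through.** **Step 1. Apply the definition to four kinds of patient.** The definition is taken from Primary safety endpoint, and the timing of NIHSS from Data collection and the Schedule of assessments.

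| Patient | CT criterion | NIHSS criterion | Result as written |
|---|---|---|---|
| A. Haemorrhage on CT, NIHSS worse by 4 or more at the 24-hour visit | met | met | event |
| B. Haemorrhage on CT, NIHSS worse by 4 or more at an unscheduled assessment, then death | met | met | event; the definition does not restrict itself to the scheduled NIHSS |
| C. Haemorrhage on CT, death before any repeat NIHSS | met | cannot be shown | non-event or missing |
| D. Death before any post-procedure CT | cannot be shown | depends on the record | not classifiable as an event |

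The gap is case C. The scheduled window opens at 24 - 6 = 18 hours, so a patient who dies earlier has a second NIHSS only if someone took an unscheduled one.

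**Step 2. Effect on the reported rate.** With n patients, e true events and k events of type C, the true rate is e/n. If type C patients count as non-events, the reported rate is (e - k)/n. If they are missing, it is (e - k)/(n - k). Both are below e/n whenever k > 0 and e < n, so either handling understates the rate.

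**Step 3. Which source supplies the endpoint.**
- If the written definition governs, case C is not counted.
- If the separate 24-hour item governs, a site can record case C as sICH, but the endpoint analysed is then not the one defined.

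These are alternatives and their effects do not add.

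**Step 4. Illustrative size.** There is no figure in the plan to reproduce: the protocol gives no sICH rate, no share of fatal cases and no power statement for sICH. The one input from the document is the planned total of 500 with 1:1 allocation, which gives 500/2 = 250 per arm. The sICH rates and the share dying before a repeat NIHSS are assumptions.

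| Assumed sICH rate | Events per arm (250 x rate) | Lost if 10% are type C | Lost if 20% are type C |
|---|---|---|---|
| 3% | 7.5 | 0.75 | 1.5 |
| 5% | 12.5 | 1.25 | 2.5 |
| 7% | 17.5 | 1.75 | 3.5 |

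The formulas of step 2 at the two ends of the table give:
- 3% with 10% lost: (7.5 - 0.75)/250 = 2.70%, or 6.75/249.25 = 2.71%.
- 7% with 20% lost: (17.5 - 3.5)/250 = 5.60%, or 14/246.5 = 5.68%.

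The mITT population excludes navigation failures, so the real number per arm will be somewhat under 250 and these counts slightly lower.

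**The case against.** **Unscheduled NIHSS.** The data list does not forbid scoring a patient who deteriorates, and such a score would satisfy the definition (case B). This stands, and it narrows the gap to deaths before any repeat NIHSS.

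**The deaths are visible elsewhere.** A reader might infer that fatal bleeds disappear from the safety data. They do not. Death is a serious adverse event reportable within 72 hours, death at 24 hours needs a narrative, and a DSMB reviews safety data. What is lost is their contribution to the primary safety comparison.

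**The SAP could handle it.** A SAP may say how a missing NIHSS is treated, and may name the source variable. But the protocol fixes the two criteria that make up sICH, and counting death as sICH changes that definition. The death criterion therefore belongs in the protocol; the question of source alone would be a minor clarification.

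**Unblinded judgement.** A reader might also infer that unblinded site staff decide sICH by a tick. The blinded core lab reads listed after "Each angiogram will be blindly assessed by the core lab for" are reperfusion scores only, and for adverse events "severity, and action taken will be evaluated by the Investigator". Even so, the protocol does not say who answers the sICH item, in what format, or whether that person knows the assignment. It provides no blinding for this item, but it does not state that the assessor is unblinded.

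**Loss of power.** It is tempting to express the effect as lost power for the safety test. The protocol claims no power for sICH, and any such figure would rest wholly on assumed rates, so none is given here.

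**Conclusion.** The point holds in a limited form. As written, the sICH definition cannot count a patient with CT-proven haemorrhage who dies before any repeat NIHSS, and the analysis section does not say whether that patient is a non-event or missing. Both readings of the definition lower the reported sICH rate. The protocol also leaves open whether its definition or the separate 24-hour item supplies the endpoint.

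The number of patients affected cannot be derived from the documents. It is probably small: about 1 to 3.5 per arm of 250, assuming sICH of 3-7% and 10-20% of cases dying before a repeat NIHSS. It still deserves correction, because this is the primary safety endpoint, the cases at issue are the most severe, and with roughly 8 to 18 expected events per arm under those assumptions a few classifications matter.

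**What to change.** In the Primary safety endpoint section, define sICH as new intracranial haemorrhage on post-procedure CT with either (a) NIHSS worsening of 4 or more points from baseline, or (b) death within the 24-hour window attributed to the haemorrhage. State whether that window closes at 24 hours or at the 30 hours that the collection window allows. The attribution is needed so that a minor haemorrhage in a patient who dies of another cause is not counted.

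State that sICH is derived from the recorded haemorrhage finding, the NIHSS values and the death or serious adverse event record. Keep the separate 24-hour sICH item as a consistency check, with disagreements queried.

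The cost is a sentence or two in the protocol and a short derivation. The haemorrhage finding, both NIHSS values and early deaths are already collected; attribution can draw on the death narrative. The reported sICH rate may be slightly higher, and attributing a death to haemorrhage needs some judgement. Deaths without a follow-up CT (case D) remain unclassified and should be listed separately by arm.
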